p. Radiology (CT or MRI scan) evaluations of tumor response: Performed during screening and during the study every 6 weeks for the first 3 months, and then every 9 weeks until discontinuation of study treatment, disease progression, death, or initiation of further systemic cancer therapy, including radiation therapy, whichever occurs earlier. CT or MRI scan will be performed within 1 week prior to the start of the next cycle. Unscheduled scan can be performed anytime, if needed to confirm disease progression. Radiology assessment for early termination/end of study, should ONLY be performed if  $\geq 9$  weeks have passed from the previous scheduled CT/MRI scan. Same assessment method and same technique should be used on each patient while on study.

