## **10 Clinical Activity Profile Assessments**

Radiology (CT or MRI scan) evaluations ( $\pm 7$  days) of tumor response are to be performed during screening within 28 days prior to Cycle 1 Day 1 (first dose of study medication), and thereafter during the study every 6 weeks for the first 3 months and then every 9 weeks until discontinuation of study treatment, disease progression, death, or initiation of further systemic cancer therapy, including radiation therapy. Radiology assessment for end of study follow-up and early termination should be performed unless the patient already has radiographic confirmation of progressive disease  $\leq 9$  weeks prior to permanent discontinuation of study drug. The same assessment method and the same technique should be used on each patient while on study.

An end-of-treatment radiology assessment should be performed unless the patient already has radiographic confirmation of progressive disease  $\leq 9$  weeks prior to permanent discontinuation of study drug. The same assessment method and the same technique should be used on each patient while on study.

Overall tumor response and progression will be evaluated by the Investigator according to RECIST 1.1.

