### **14.1 Determination of Sample Size**

This is a 2-part study: Part A (Dose-Escalation) and Part B (Cohort-Expansion).

Up to 30 patients were to have been enrolled in the 3+3 dose-escalation portion of the study (Part A).

The cohort-expansion portion of the study (Part B) will enroll up to 57 patients based on Simon's two-stage design. The first stage will recruit up to 9 patients in each of three cohorts. If at least 1 objective response is observed, a second stage recruitment will occur with up to 10 additional patients enrolled into that cohort, for a total of up to 19 patients per cohort. If at least 4 objective responses are observed in the 19 patients, then OBI-999 will be considered worthy of further evaluation in that indication. Patients will be followed up to the 24-week scheduled response assessment for the purposes of counting objective responses for Simon's two-stage design success criteria. This design is based on a level of low interest for a treatment with an ORR of 10% versus a level of high interest for a treatment with an ORR of 25%. The sample size is based on a one-sided alpha of 0.12 and 72% power. The two-stage design limits the number of patients treated for a treatment with low levels of activity.

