### **14.3 Clinical Activity Analysis**

ORR is defined as the percentage of patients with confirmed partial response (PR) or complete response (CR) based on tumor assessment as determined by RECIST 1.1. A confirmed response will be defined as two or more consecutive assessments separated by at least 3 weeks. Patients who discontinue due to toxicity or clinical progression prior to post-baseline tumor assessments will be considered as non-responders and retained in the denominator.

CBR is defined as the percentage of patients with confirmed CR, PR, or stable disease. A confirmed response will be defined as two or more consecutive assessments separated by at least 3 weeks. Patients who discontinue prior to post-baseline tumor assessments will be considered as non-responders and retained in the denominator.

DOOR is defined as time from date of reported confirmed PR or CR to the date of progression, and will be summarized descriptively using time-oriented summary statistics. Additionally, a listing of DOOR for those patients experiencing response will be provided.

PFS is defined as the time from first dose of study drug until radiographically determined disease progression or death due to any cause, whichever occurs first. Patients who are still alive or who have no progressive disease reported at analysis, will be censored at their last evaluable tumor assessment.

Kaplan Meier estimates and 95% confidence intervals will be presented for time-to-event endpoints such as PFS, if sufficient numbers of events to calculate meaningful statistics are observed.

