10.3 HANDLING OF MISSING DATA

Partial or missing start and end dates of AEs and concomitant medications will be imputed conservatively based on the rule described in Appendix II: Imputation rules for missing dates. The imputed dates will be used to allocate the AEs and concomitant medications to a study period, and to determine whether an AE is/is not treatment emergent. Listings of the AEs and concomitant medications will present the actual partial dates; imputed dates will not be shown in the listings.

For ORR endpoint, patients with missing data (for any reason) will be included as non-responders in the statistical analysis for each related follow-up analysis. For analyses performed in the safety population, patients who discontinue due to toxicity or clinical progression prior to post-baseline tumor assessments will be considered as non-responders and retained in the denominator.

For CBR endpoint, patients with missing data (for any reason) will be included as non-responders in the statistical analysis for each related follow-up analysis.

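### Scheduled scans end with study drug, and the protocol's two rules for the one remaining scan contradict each other, so whether a response can be confirmed may depend on which rule a site follows

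*Protocol*

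**What the plan says.** **Counting and confirmation.** Protocol Section 14.1: "Patients will be followed up to the 24-week scheduled response assessment for the purposes of counting objective responses". Section 14.3: "A confirmed response will be defined as two or more consecutive assessments separated by at least 3 weeks". SAP Section 10.7.1 repeats the confirmation rule.

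**End of scheduled scanning.** Footnote p of Table 9-1 continues scans, "then every 9 weeks until discontinuation of study treatment, disease progression, death, or initiation of further systemic cancer therapy". Section 10 has the same end point: "every 9 weeks until discontinuation of study treatment, disease progression, death, or initiation of further systemic cancer therapy". The synopsis and the SAP's Appendix I agree. Stopping drug ends the series even without progression or new therapy.

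**The one remaining scan.** Table 9-1 marks radiology in the end-of-study/early-termination column, and the end-of-study visit is 28±7 days after the last dose. Footnote p, which the SAP reproduces, permits this scan only when at least 9 weeks have gone by since the previous scheduled one. Section 10 calls for it unless progression was already shown radiographically no more than 9 weeks before permanent discontinuation.

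**Classification.** In the SAP 10.7.1 best-response table, a PR or CR followed only by non-evaluable time points becomes SD, or NE if the minimum SD duration is not met. SAP Section 10.3 adds that for ORR "patients with missing data (for any reason) will be included as non-responders in the statistical analysis". Protocol Section 14.3 has its own non-responder rule, but it covers only patients who stop for toxicity or clinical progression before any post-baseline scan.

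**Abbreviated report.** SAP Section 11 keeps ORR in the safety population and a waterfall plot, and drops CBR, DOR and PFS.

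**The concern.** A responder who permanently stops OBI-999 without progressing, between the first response and its confirmation, can be recorded as a non-responder because no confirming scan was made, not because the response failed. Table 8-1 ends treatment for Grade 4 toxicity, so the loss is tied to tolerability and mixes toxicity into the activity rate. It runs one way: a missing scan can remove a confirmed response but cannot create one. A patient with SD who stops has, in the same way, at most one further scan on which a response could be seen.

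The contradiction adds a second problem. Two sites that each follow a passage of the same protocol can classify the same patient differently. With 9 patients per cohort in stage 1 and a go rule of one response, a single lost confirmation could have closed a cohort. In the abbreviated report, a reader cannot separate lack of activity from lack of a confirming scan.

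**Working it through.** **1. The plan's own figure.** Inputs from Protocol Section 14.1: "The first stage will recruit up to 9 patients in each of three cohorts"; go on with at least 1 response in 9; success with at least 4 in 19; ORR 10% versus 25%; "The sample size is based on a one-sided alpha of 0.12 and 72% power".

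The exact probability of success at response rate p is

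P(p) = Σ (x = 1 to 9) Bin(x; 9, p) × Pr[Y ≥ max(0, 4 − x)], with Y ~ Bin(10, p).

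P(0.10) = 0.110 and P(0.25) = 0.720. The power reproduces, and 0.12 acts as a ceiling on alpha. The chance of stopping at stage 1 is (1 − p)^9: 0.387 at 10% and 0.075 at 25%.

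**2. Can the remaining scan confirm a response?** Doses fall every 3 weeks. Nominal scans fall at weeks 6, 12, 21 and 30. The end-of-study visit is nominally 4 weeks after the last dose, so gap = (last dose + 4) − week of first response.

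| First PR/CR (week) | Last dose (week) | Gap in weeks (visit window) | Footnote p | Section 10 |
|---|---|---|---|---|
| 6 | 3 | 1 (0–2) | barred | done, too early to confirm |
| 6 | 6 | 4 (3–5) | barred | done, can confirm |
| 6 | 9 | 7 (6–8) | barred | done, can confirm |
| 12 | 9 | 1 (0–2) | barred | done, too early to confirm |
| 12 | 12 | 4 (3–5) | barred | done, can confirm |
| 12 | 15 | 7 (6–8) | barred | done, can confirm |
| 12 | 18 | 10 (9–11) | allowed, can confirm | done, can confirm |

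In four of the seven rows the two rules give opposite results. Footnote p also lets a scan be taken up to 1 week before the next cycle. That can lengthen a gap by 1 week, so the 7-week rows reach 9 weeks only if the scan is a full week early and the visit a full week late.

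**3. Size if responders are lost.** The documents give no loss rate. Let L be the assumed share of true responders left unconfirmed for this reason. The counted ORR is then p(1 − L). L is taken as equal under both hypotheses.

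| L | Counted ORR, true 25% | Shortfall (points) | Power | Stage 1 stop, true 25% | Type I error, true 10% |
|---|---|---|---|---|---|
| 0 | 25.0% | 0 | 72.0% | 7.5% | 0.110 |
| 5% | 23.75% | 1.25 | 67.7% | 8.7% | 0.095 |
| 10% | 22.5% | 2.5 | 63.1% | 10.1% | 0.081 |
| 20% | 20.0% | 5.0 | 52.9% | 13.4% | 0.057 |

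For example, at L = 10%: 0.25 × 0.90 = 0.225 and P(0.225) = 0.631.

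**The case against.** **Section 10 rescues many cases.** This stands. A patient with a PR at week 6 who took the week 6 dose and stops at week 8 has the end-of-study visit nominally at week 10, 4 weeks after the scan. A scan there can confirm. The loss is not automatic; it depends on footnote p being followed, or on the last dose having come a cycle before the response scan.

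**The SAP already has an unconfirmed-response analysis.** This stands in part. SAP 10.7.1 presents unconfirmed ORR if it differs from confirmed ORR by 10%. It does not say whether that is absolute or relative, or per cohort or pooled. On an absolute reading, one patient in 9 triggers it (1/9 = 11.1 points), but one in 11 does not (1/11 = 9.1 points); a cohort would have 11 if nine places were filled and two replacements added. The analysis also mixes responses that a later scan failed to confirm with responses never rescanned. SAP Section 11 does not say whether it is kept. The waterfall plot is kept and does not depend on confirmation, but it shows target-lesion change only.

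**The group is narrow.** This stands. Table 8-1 holds the dose for Grade 2 and 3 toxicity, and a patient on hold has not discontinued, so scans continue. Only permanent stops without progression in the confirmation gap matter.

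**The assumed 25% and 10% may already be rates under this schedule.** ORR is defined as confirmed response, so subtracting L could double count. Section 14.1 does not say where the rates come from, so this cannot be excluded.

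**Recording an unconfirmed PR as SD or NE follows the SAP's cited response criteria.** True. The point is the missing opportunity to confirm, not the classification.

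**Conclusion.** The point holds. Scheduled scanning stops with study drug although responses are counted to 24 weeks, and footnote p contradicts Section 10 on the only scan left. Under footnote p, a first response at week 6 or 12 with a permanent stop at that point or one cycle later nominally cannot be confirmed; under Section 10 it often can. Any effect lowers confirmed ORR and, with it, both power and type I error. The fall from 72% to about 68%–53% rests wholly on an assumed 5%–20% loss.

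A reader might infer that all scanning ends with the drug, so that every patient who stops for toxicity before confirmation becomes a non-responder and the design has in fact lost power. The documents do not support that. Section 10 requires a further scan, no loss rate is given, and SAP Section 5.4 records that the go/no-go analysis never took place. What remains is a possible downward bias, of unknown size, in the one Part B efficacy rate kept for the abbreviated report. The same section reports four patients without a post-baseline RECIST assessment at the end of stage 1. That shows tumor assessment was incomplete, but no reasons are given, so it is not evidence of this mechanism.

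**What to change.** **Protocol wording, for this design or any reuse of it.** Reconcile footnote p (and its SAP copy), Section 10 and the synopsis with Section 14.1. Patients who stop OBI-999 without progression or new anticancer therapy should stay on the existing scan schedule until progression, new therapy, death, withdrawal of consent or the 24-week count, whichever comes first. Remove the 9-week bar where a response awaits confirmation. State which scan closes the count, since nominal scans fall at weeks 21 and 30 and none at week 24. The cost is wording in a few places and one or two off-treatment scans in few patients. Some will decline, so a few responses will remain unconfirmed.

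**SAP Section 10.7.1, for data already collected.** For each Part B cohort, and whatever the 10% trigger shows, report the number of patients with an unconfirmed CR or PR who stopped drug without progression and had no later evaluable scan. Show ORR with these patients counted as responders, labeled as an upper bound beside the confirmed ORR. This costs one row and one extra estimate per cohort, with no new data. With the study stopped, this is the part that can still change what is reported.

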**Table 9-2 Part A - Pharmacokinetic and ADA Sampling Schedule**

Cycle	Cycle 1 and Cycle 2						Cycle 3 and Cycle 4		Cycle 5-8, 12 and every 4 cycles thereafter	EoS / ET
	D1	D2	D4	D8	D11	D15	D1	D8		
Cycle Day										±7 days
Pharmacokinetic Samples										
Before infusion	X a						X b		X b	
30 minutes after end of infusion (90 min) c	X	X d	X	X d	X	X				
2 hours after end of infusion (180 min) c,e	X									
4 hours after end of infusion (300 min) c,e	X									
8 hours after end of infusion (540 min) c,e	X									
Immunogenicity Studies (ADA)f	X						X		X	X

Abbreviations: ADA = anti-drug antibody; C = Cycle; D = Day; EoS = End of Study; ET = Early Termination; min = minute

OBI-999 infusion should be administered on Day 1 of every 21-day cycle throughout the study treatment period.

The infusion duration of Cycle 1 and Cycle 2 are  $60 \pm 10$  minutes and can be reduced to  $30 \pm 10$  minutes from Cycle 3, if there were no infusion related adverse events on prior infusions and at the discretion of the Investigator.

- Cycle 1 Day 1 (C1D1) pre-infusion serum samples can be drawn within 1 day prior-to the infusion.
- Pre-infusion serum samples can be collected at any time prior to the infusion on the day of the infusion.
- Post-infusion samples on D1 can be collected in a window of  $\pm 15$  minutes.
- Samples on Days 2, 4, 8, 11, and 15 can be collected in a window of  $\pm 2$  hours based on the end of infusion on Day 1.
- If there is change of the infusion rate or interruption of infusion, the PK sampling on Day 1 is to be collected from the exact time of completion of infusion to obtain the post-infusion samples after the end of infusion. Exact time of sample collection and the reason for interruption should be documented in the eCRF.
- ADA samples will be collected along with pre-infusion PK samples. No post-infusion ADA samples will be collected. For subjects with persistent antibodies at end of study, an additional ADA sample will be collected at 4 months after the end of study visit.

**Table 9-3 Part B - Pharmacokinetic and ADA Sampling Schedule**

Cycle	Cycle 1 and Cycle 2					Cycle 3, Cycle 4, Cycle 8, and Every 4 Cycles Thereafter	EoS / ET
	D1	D2	D4	D8	D15		
Cycle Day						D1	$\pm 7$ days
Pharmacokinetic Samples							
Before infusion	X a					X b	
30 minutes after end of infusion (90 min) c	X	X d,g	X d,g	X d	X d	X	X
6 hours after end of infusion (420 min) c,e	X						
Immunogenicity Studies (ADA)f	X					X	X

Abbreviations: ADA = anti-drug antibody; C = Cycle; D = Day; EoS = End of Study; ET = Early Termination; min = minute

OBI-999 infusion should be administered on Day 1 of every 21-day cycle throughout the study treatment period.

The infusion duration of Cycle 1 and Cycle 2 are  $60 \pm 10$  minutes, and can be reduced to  $30 \pm 10$  minutes from Cycle 3, if there were no infusion related adverse events on prior infusions and at the discretion of the Investigator.

- Cycle 1 Day 1 (C1D1) pre-infusion serum samples can be drawn within 1 day prior-to the infusion.
- Pre-infusion serum samples can be collected at any time prior to the infusion on the day of the infusion.
- Post-infusion samples on D1 can be collected in a window of  $\pm 15$  minutes.
- Samples on Days 2, 4, 8, and 15 can be collected in a window of  $\pm 2$  hours based on the end of infusion on Day 1.
- If there is change of the infusion rate or interruption of infusion, the PK sampling on Day 1 are to be collected from the exact time of completion of infusion to obtain the post-infusion samples after the end of infusion. Exact time of sample collection and the reason for interruption should be documented in the eCRF.
- ADA samples will be collected along with pre-infusion PK samples. No post-infusion ADA samples will be collected. For subjects with persistent antibodies at end of study, an additional ADA sample will be collected at 4 months after the end of study visit.
- This intensive PK sampling will be collected from first 5 patients in each cohort.

## **10 Clinical Activity Profile Assessments**

Radiology (CT or MRI scan) evaluations ( $\pm 7$  days) of tumor response are to be performed during screening within 28 days prior to Cycle 1 Day 1 (first dose of study medication), and thereafter during the study every 6 weeks for the first 3 months and then every 9 weeks until discontinuation of study treatment, disease progression, death, or initiation of further systemic cancer therapy, including radiation therapy. Radiology assessment for end of study follow-up and early termination should be performed unless the patient already has radiographic confirmation of progressive disease  $\leq 9$  weeks prior to permanent discontinuation of study drug. The same assessment method and the same technique should be used on each patient while on study.

An end-of-treatment radiology assessment should be performed unless the patient already has radiographic confirmation of progressive disease  $\leq 9$  weeks prior to permanent discontinuation of study drug. The same assessment method and the same technique should be used on each patient while on study.

Overall tumor response and progression will be evaluated by the Investigator according to RECIST 1.1.

## **11 Pharmacokinetics**

### **11.1 Pharmacokinetic Sampling**

Blood samples for PK analysis of OBI-999 levels will be collected at the time points indicated in the Pharmacokinetic and ADA Sampling Schedules (see [Table 9-2](#) [Part A] and [Table 9-3](#) [Part B]). The actual date and time of each blood sample collection will be recorded. The timing of PK samples may be altered and/or PK samples may be obtained at additional time points to ensure thorough PK monitoring.

Details of PK blood sample collection, processing, storage, and shipping procedures are provided in a separate laboratory manual.

### **11.2 Pharmacokinetic Analytical Methodology**

The concentrations of OBI-999 total antibody, ADC, and MMAE will be determined from the serum samples using a validated analytical method. Details of the method validation and sample analysis will be included with the final clinical study report.

Pharmacokinetic parameters will be calculated using a non-compartmental method from the PK samples collected during Cycles 1 and 2 and will include but will not be limited to  $C_{max}$ , AUC, elimination half-life ( $t_{1/2}$ ), clearance (Cl), time to reach maximum concentration ( $T_{max}$ ), and volume of distribution ( $V_d$ ).

Pharmacokinetic methods may also be applied to further investigate OBI-999 exposure (e.g., accumulation of OBI-999, presence of dose- or time-dependent OBI-999 PK behavior, verification of influential factors on OBI-999 PK).

## **12 Safety Assessments**

Safety assessments (vital signs, physical examinations, electrocardiogram [ECG] recording, AEs, ECOG, ophthalmology, clinical laboratory results [routine hematology, serum chemistry, coagulation, and urinalysis], and immunogenicity [ADAs]) are to be performed at protocol-specified visits, as specified in the Schedule of Assessments, [Table 9-1](#).

### **12.1 Vital Signs**

Vital signs (body temperature, heart rate, systolic, and diastolic blood pressure measurements) will be evaluated at the visits indicated in the Schedule of Assessments ([Table 9-1](#)). All vital signs will be measured after the patient has been resting for at least 5 minutes. Blood pressure measurements are to be taken in the same arm for the duration of the study. Temperature measurement will be obtained as clinically indicated.

Body weight (without shoes) will be recorded whenever vital signs are recorded, and height (without shoes) will be recorded at screening only.

Vital sign measurements will be repeated if clinically significant or machine/equipment errors occur. Out-of-range blood pressure, respiratory rate or heart rate measurements will be repeated at the Investigator's discretion. Any confirmed, clinically significant vital sign measurements must be recorded as AEs.

### **12.2 Physical Examination**

A complete physical examination (head, eyes, ears, nose, throat [HEENT], heart, lungs, abdomen, skin, cervical and axillary lymph nodes, neurological, and musculoskeletal systems) will be performed at screening and early termination. Medical history will be recorded at screening, including smoking history, if applicable.

A limited physical examination to verify continued patient eligibility and to follow up any change in medical history will be performed at the visits indicated in the Schedule of Assessments ([Table 9-1](#)). Symptom-driven limited physical examinations will be performed as clinically indicated at any study visit. All changes not present at baseline or described in the past medical history and identified as clinically noteworthy must be recorded as AEs.

Physical examinations should include an assessment for signs and symptoms of peripheral neuropathy as this is a known adverse event associated with MMAE-based ADCs and may be expected to occur with OBI-999.

As potential retinal and corneal findings were observed at the highest dose in the rat multiple dose toxicology study, ophthalmology examinations will be conducted as indicated in the Schedule of Assessments ([Table 9-1](#)) to document any treatment-emergent changes.

Medical history will include previous cancer therapies, cancer history, and past and ongoing concomitant illnesses.

